#### Pregnancy and SAE reconciliation

Pregnancies and SAEs captured within the registry database will be reconciled with the pregnancy and SAE information submitted to Novartis in order to ensure that all relevant information was received. Full details regarding the frequency, methodology and resolution of pregnancy and SAE reconciliation is detailed in the registry data management plan.

## 5 Statistical analysis

#### 5.1 Statistical methods

Descriptive statistics will be used to summarize the findings; specifically, overall frequency (proportion, 95% confidence interval) of major malformations will be calculated, as well as frequencies of specific outcomes, e.g., heart defect, spina bifida, club foot deformity, cleft palate. The same will be calculated for minor congenital malformations, spontaneous abortions, stillbirths, elective terminations, adverse effects on immune system development, and any other adverse pregnancy outcomes. Minor anomalies will be grouped and reported as "defects case", if three or more occur in the same child. All primary analyses will be restricted to prospectively identified cases with outcome information available. Retrospectively identified cases (refer to Section 3.1 for description) will be collected and analyzed; however, these cases will not be included in any outcome rates calculated for the primary analysis. Multiple and singleton gestations will be presented separately.

The frequency of major malformations in the proposed registry will be compared to the frequency of major malformations in infants in the external comparison groups, i.e., MACDP (CDC) for US data, EUROCAT for European cases and data collected by external investigators including data made available from other registries that include pregnancy exposure and outcome information. Furthermore, using an internal comparison approach (if enough data is available), the risk of congenital anomalies among women with first trimester exposure will be compared with risks of congenital anomalies among women with second and third trimester exposure to investigate if there is an increased risk (risk estimate, 95% confidence interval) of major malformations among infants exposed to fingolimod.

In order to assess the overall generalizability and representativeness of the data included in this registry demographics of the registry population and the population of all pregnancy cases reported to pharmacovigilance will be summarized.

[figure not shown]

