## 5.2 Sample size determination

In the US 3,030 infants with birth defects per 100,000 live births were reported by CDC (2010). The European surveillance of congenital anomalies (EUROCAT) reported a prevalence rate of 2334.2 per 100,000 live births (EUROCAT 2010). Worldwide about 6% of all newborn infants have serious birth defects of genetic or partially genetic origin and the annual prevalence of congenital malformations was 3,650 per 100,000 births (Christianson et al 2006).

The following chart (Figure 5-1) shows the power of this registry based on different numbers of women included to detect at least a 50% to 100% increased risk of any major malformation. Based on this assumptions the study will have >80% power (two-sided test,  $\alpha$  set at 0.05) to detect a 80% risk increase if 500 women are included assuming a background prevalence of major malformations of 3% (nQuery Advisor 5.0).

Although it is expected that up to 500 women may potentially be enrolled during the at least four year recruitment period of the study, the rate of enrollment will not be known until actual accrual of patients begins (for details for the reasons for discontinuing this pregnancy registry refer to Section 3).

Figure 5-1 Power based on number of included women (N) to detect a 50% to 100% risk increase based on a background prevalence of 3%

Although designed primarily as a prospective registry, the registry will accept retrospective reports of pregnancy outcome, meaning cases initially reported to the registry after the outcome is known. Similar to passive spontaneous case reporting, these reports may contribute to the differential reporting of poor outcomes but may also provide important information. The registry will allow for retrospective reports to be differentiated from prospective reports and analysis will be done separately. Although these cases do not contribute to the evaluation of true event rates in the exposed population, these cases may still provide important information.

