## 6.1 Registry enrollment

#### 6.1.1 Type of registry sites

Two different types of sites will be targeted for recruitment:

- National Coordinating Site (NCS): Acts as Principal Investigator with IRB/EC/HA approvals and contract. Will enroll and follow-up patients at their own site, and coordinate enrollment at Sentinel Sites. In the US and Canada the CRO will act as a NCS.
- Sentinel Site (SS): Will be recognized as such and set up only after they have an eligible patient. Depending on the decision of the investigator a SS can act as a Co-Investigator of the NCS or they can be set up as independent Principal Investigators.

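### The >80% power in Section 5.2 is for all 500 women against one 3% background, but the external comparisons are assigned by region, and the stated power does not carry over to them

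*Protocol*

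**What the plan says.** Protocol Section 5.2 claims that "the study will have >80% power (two-sided test", with alpha "set at 0.05) to detect a 80% risk increase". The basis is one cohort and one background: "to detect a 80% risk increase if 500 women are included assuming a background prevalence of major malformations of 3" per cent.

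The same section quotes different regional backgrounds. For the US it gives "3,030 infants with birth defects per 100,000 live births were reported by CDC (2010"). For Europe, EUROCAT "reported a prevalence rate of 2334.2 per 100,000 live births". It also quotes a worldwide figure of 3,650 per 100,000 births.

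Section 5.1 lists the external comparison groups as "MACDP (CDC) for US data, EUROCAT for European cases and data collected by external investigators", the last of these including data from other registries. Section 3.5 likewise gives MACDP to US cases and EUROCAT to European cases, and leaves open the use of other national surveillance groups. Neither section says how the regional comparisons combine into one result.

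Canada also enrols: "In the US and Canada the CRO will act as a NCS" (Section 6.1.1). No reference source is named for Canadian cases.

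**The concern.** The power statement and the comparison plan describe different things. Section 5.2 treats the registry as a single sample tested against 3%. Sections 3.5 and 5.1 match each region to its own reference, and the European reference quoted is clearly below 3%. A lower background means fewer expected cases and less power at the same ratio. Dividing the cohort reduces power further.

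The stated goal in Section 2 is to compare outcomes with background frequencies, and the findings are meant for counselling. A reader who trusts the figure above 80% could take a regional result that shows no increase as more reassuring than it is.

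**Working it through.** **Inputs.** From Section 5.2: n = 500, ratio 1.8, two-sided alpha 0.05, p0 = 3%; quoted backgrounds 3.03% (US), 2.3342% (EUROCAT) and 3.65% (worldwide). Assumptions: the CDC figure stands for MACDP; every woman is evaluable; the regional split, which the protocol does not give, is varied.

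**Formula (large-sample, one proportion against a fixed rate).** With p1 = 1.8 × p0,

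power = Φ{[(p1 − p0)√n − 1.96√(p0(1 − p0))] / √(p1(1 − p1))}.

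**Step 1: the protocol's own figure.** p0 = 0.03, p1 = 0.054, n = 500:

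- (p1 − p0)√n = 0.024 × √500 = 0.5367
- 1.96√(0.03 × 0.97) = 0.3343
- √(0.054 × 0.946) = 0.2260
- (0.5367 − 0.3343)/0.2260 = 0.895, so power = 81.5%.

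This agrees with the stated figure. The exact binomial test rejects at 24 or more cases (upper tail 0.0179) and has 75.1% power. The exact Poisson version (expected 15) has 74.4%.

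**Step 2: regional reading.** For 250 US cases (p1 = 5.454%): (0.3833 − 0.3360)/0.2271 = 0.208, power 58.3%. For 250 European cases (p1 = 4.2016%): (0.2953 − 0.2959)/0.2006 = −0.003, power 49.9%. Other sizes, large-sample / exact binomial:

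| Cases in region | US vs 3.03% | Europe vs 2.334% |
|---|---|---|
| 150 | 43.2% / 30.3% | 36.9% / 18.1% |
| 250 | 58.3% / 49.8% | 49.9% / 36.0% |
| 350 | 69.8% / 63.4% | 60.5% / 50.5% |
| 500 | 81.8% / 76.7% | 72.8% / 62.0% |

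Large-sample 80% power needs 473 US cases or 620 European cases, 1,093 in total against 500 planned. So no split of 500 reaches 80% in both regions, and Europe misses it even if all 500 women were European.

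**Step 3: pooled, region-matched reading.** Expected count E = n(US) × 0.0303 + n(Europe) × 0.023342 + n(other) × 0.0365, and p0 = E/500. Using 3.65% for other countries is an assumption.

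| US / Europe / other | E | p0 | Large-sample | Exact Poisson |
|---|---|---|---|---|
| 375 / 125 / 0 | 14.28 | 2.856% | 79.8% | 73.0% |
| 250 / 250 / 0 | 13.41 | 2.682% | 77.7% | 69.6% |
| 125 / 375 / 0 | 12.54 | 2.508% | 75.3% | 65.8% |
| 200 / 200 / 100 | 14.38 | 2.876% | 80.1% | 74.1% |
| 150 / 200 / 150 | 14.69 | 2.938% | 80.8% | 70.9% |

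The exact values do not move smoothly with E because the rejection limit is a whole number. The fair comparison is within one method: 81.5% falls to 75.3-79.8% large-sample for the three US/Europe mixes, and 74.4% falls to 65.8-73.0% exact Poisson.

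**The case against.** The strongest reply is that the text assigns reference sources by region without saying that the comparisons are separate. Section 5.1 speaks of the registry's frequency of major malformations as a whole, so pooling is not ruled out. How sources are combined, and which source each country receives, is ordinarily left to a statistical analysis plan. On planning values, 3% is not unreasonable for a multinational cohort: the simple mean of the three quoted rates is (3.03 + 2.334 + 3.65)/3 = 3.005%. The primary objective is descriptive, and no regional hypothesis test is laid down.

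Much of this stands, and it limits the point. Four stronger readings are tempting, and the protocol does not support them:

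- *That the plan definitely splits the cohort into two separate tests.* This is an inference. The pooled reading is open, which is why both are worked through.
- *That Canadian and other women have no comparator.* Section 5.1 allows external and other registry data without regional limit, and Section 3.5 allows other national sources. None is named for these countries, but they are not excluded, and they count in the overall frequency.
- *That a European increase would be hidden by a flat 3% reference.* The plan matches European cases to EUROCAT, so it does not make that comparison.
- *That the calculation in Section 5.2 is wrong.* It is correct for its own inputs.

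The reply does not remove the mismatch. The power claim is made in the protocol itself, and it fits neither the regional reading nor most US/Europe mixes of the pooled one.

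**Conclusion.** The point holds as a mismatch between the stated power and the region-assigned comparisons. On the regional reading the shortfall is large: about 58% (US) and 50% (Europe) at an assumed 250/250, and no split gives 80% in both. On the pooled reading it is small: about 75-80% large-sample with a quarter to three quarters European, and 80-81% in the two mixes tried with 100 or 150 women from elsewhere at 3.65%. Exact power is lower in every case, but so is the protocol's own (about 75%), so that part of the gap comes from the choice of test and not from the regional assignment.

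The regional mix is assumed throughout; the conclusion that both regions cannot reach 80% does not depend on it. Section 5.1 restricts the primary analyses to prospective cases with known outcome, so 500 evaluable cases is a favourable assumption. The descriptive estimate of overall frequency is not affected. The change is worth making because it is nearly free and gives the power statement a defined comparison to refer to.

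**What to change.** Make the main external comparison one pooled observed/expected ratio. The expected count is the sum over regions of evaluable outcomes times that region's matched reference rate, reported with an exact Poisson 95% confidence interval. Keep US against MACDP and Europe against EUROCAT as descriptive regional results. In Section 5.2, restate the power for the pooled ratio over a range of regional mixes and say whether it is large-sample or exact. Name a reference for Canada and every other participating country in advance; this is needed to compute the expected count and is not a separate error.

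The cost is wording and simple programming, with no new data collection. The downside is that a pooled ratio assumes a broadly common relative effect across regions, which the regional results let readers check.

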## 5.2 Sample size determination

In the US 3,030 infants with birth defects per 100,000 live births were reported by CDC (2010). The European surveillance of congenital anomalies (EUROCAT) reported a prevalence rate of 2334.2 per 100,000 live births (EUROCAT 2010). Worldwide about 6% of all newborn infants have serious birth defects of genetic or partially genetic origin and the annual prevalence of congenital malformations was 3,650 per 100,000 births (Christianson et al 2006).

The following chart (Figure 5-1) shows the power of this registry based on different numbers of women included to detect at least a 50% to 100% increased risk of any major malformation. Based on this assumptions the study will have >80% power (two-sided test,  $\alpha$  set at 0.05) to detect a 80% risk increase if 500 women are included assuming a background prevalence of major malformations of 3% (nQuery Advisor 5.0).

Although it is expected that up to 500 women may potentially be enrolled during the at least four year recruitment period of the study, the rate of enrollment will not be known until actual accrual of patients begins (for details for the reasons for discontinuing this pregnancy registry refer to Section 3).

Figure 5-1 Power based on number of included women (N) to detect a 50% to 100% risk increase based on a background prevalence of 3%

Although designed primarily as a prospective registry, the registry will accept retrospective reports of pregnancy outcome, meaning cases initially reported to the registry after the outcome is known. Similar to passive spontaneous case reporting, these reports may contribute to the differential reporting of poor outcomes but may also provide important information. The registry will allow for retrospective reports to be differentiated from prospective reports and analysis will be done separately. Although these cases do not contribute to the evaluation of true event rates in the exposed population, these cases may still provide important information.

Prenatal exposure will be summarized by trimester(s) exposed as well as exposure up to 8 weeks before LMP, dose and regimen. Exposures at specific gestational ages (in weeks) will be evaluated for individual cases. Exposure to other drugs and biologics will be collected, and HCPs will be able to indicate if there is a suspected, probable or known cause for any adverse pregnancy outcome. Trimesters will be defined as < 14 weeks (1st trimester), 14 to 27 weeks (2nd trimester) and  $\ge 28$  weeks (3rd trimester).

Spontaneous pregnancy loss will be defined as pregnancy loss at < 20 weeks gestation. Gestational age corrected by ultrasound will be used for gestational age when available, otherwise gestational age based on LMP will be used. Stillbirth (fetal death) will be defined as any pregnancy loss at  $\ge 20$  weeks gestation.

Low birth weight (LBW) is defined as < 2500 grams (5 pounds, 8 ounces) at birth and very low birth weight (VLBW) is defined as < 1500 grams (3 pounds, 4 ounces). Intrauterine growth retardation (IUGR) will be defined as estimated fetal weight below the 10th percentile for gestational age. It is important to note, however, that as many as 70% of fetuses who are estimated to weigh below the 10th percentile for gestational age are small simply due to constitutional factors such as female sex or maternal ethnicity, parity, or body mass index (Manning 1995). This definition covers all small for gestation fetuses and does not make a distinction among fetuses who are constitutionally small, growth restricted and small, and growth restricted but not small; therefore, any report of IUGR in the exposed population will require further assessment to ensure the case is appropriately categorized. In addition, cases where the physician has reported decreased relative growth even though the infant is > 10th percentile, may be included in the overall analysis of potential in-utero growth restriction. Moderate and severe IUGR will be defined as fetal weight in the 3rd to 10th percentile and less than 3rd percentile, respectively (Peleg et al 1998). For infants, the same criteria (i.e., weight below the 10th percentile for gestational age) will be applied but referenced as small for gestational age (SGA) at birth. An infant who is larger than expected for the age and gender, with a birth weight above the 90th percentile, will be considered large for gestational age (LGA).

Structural and functional congenital anomalies identified in the perinatal period through one year of age will be collected and classified. The registry will utilize congenital anomaly definitions and classifications consistent with the MACDP and the EUROCAT surveillance programs (i.e., ICD9 or ICD10-BPA), to the extent possible, in order to facilitate comparisons (details regarding coding and classification, and case definition, will be established in registry-specific clinical review procedures). Both coding methods will be utilized.

Chromosomal abnormalities (and genetic disorders) will be evaluated separately due to the low likelihood that these defects would be associated with drug exposure. Defects identified outside of the study period may also be reported to the registry, but it is not the intention of the registry to pursue long-term data (> one year) regarding the offspring. All congenital anomalies reported will be reviewed periodically by a clinical reviewer who will determine whether additional follow-up with the reporting physician is required in order to classify the event (including classification into minor or major anomalies), and will review the coded datasets overall for accuracy and internal consistency. The calculation for risk of congenital malformations will be made by dividing the number of congenital anomalies associated with any pregnancy outcome by the sum of the number of live births without congenital anomalies and any outcomes involving congenital anomalies. Estimates of risk will also be analyzed as stratified by trimester of exposure.

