## **Amendment 3 (10-Dec-2019)**

#### Amendment rationale

The rationale for this amendment is to reflect the update in the Gilenya (fingolimod) core datasheet or local product information regarding use of fingolimod in pregnancy.

At the time of writing this amendment, 260 patients were enrolled in the registry.

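### The >80% power in Section 5.2 is stated for 500 women who may be enrolled, with no allowance for the smaller set that forms the primary malformation rate

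*Protocol*

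**What the plan says.** Section 5.2 states that "the study will have >80% power (two-sided test", at alpha 0.05, "to detect a 80% risk increase if 500 women are included assuming a background prevalence of major malformations of 3" per cent. The caption of Figure 5-1 uses the same unit: "Power based on number of included women (N) to detect a 50% to 100% risk increase based on a background prevalence of 3" per cent. The next paragraph of Section 5.2 shows what the 500 stands for: "Although it is expected that up to 500 women may potentially be enrolled during the at least four year recruitment period of the study". It adds that the enrolment rate can only be learned once women start to be accrued.

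The analysis is defined on a smaller set:

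- **Section 5.1:** "All primary analyses will be restricted to prospectively identified cases with outcome information available". Retrospective cases are kept out of the primary outcome rates.
- **Section 3.1:** retrospective cases may nevertheless enrol, so they count towards an enrolment total.
- **The risk calculation that closes Section 5** (Section 5.3 in the table of contents): the number of anomalies is divided "by the sum of the number of live births without congenital anomalies and any outcomes involving congenital anomalies". Spontaneous losses, stillbirths and terminations without an anomaly are therefore not in the denominator.

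On accrual, the rationale for Amendment 3 (10 December 2019) records: "At the time of writing this amendment, 260 patients were enrolled in the registry". Amendment 2 (5 July 2012) records one.

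**The concern.** The N in the power statement is not the N of the analysis it is meant to support. The protocol itself provides for retrospective enrolments, losses to follow-up, spontaneous losses and terminations. Each of these reduces the evaluable number, and none is allowed for in Section 5.2. The section even says that retrospective cases add nothing to the estimation of true event rates, but does not carry this into the sample size.

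The accrual text has a related fault. The current version carries both the December 2019 count and a sentence written as though accrual had not begun.

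What is at stake is how the comparison with the external surveillance systems is read. Section 5.2 gives the only sample-size justification in the protocol, and Section 2 says the findings will be used in counselling patients. If the comparison shows no clear excess, a reader will judge it against the stated >80%. The evaluable set may give noticeably less.

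**Working it through.** **Inputs.** From Section 5.2: background p0 = 0.03; 80% increase, so p1 = 1.8 × 0.03 = 0.054; two-sided alpha 0.05 (z = 1.96); n = 500. From Section 5.1: the comparison is with external surveillance rates, so it is treated as one sample against a fixed reference rate. From Amendment 3: 260 enrolled. The evaluable share is not in the protocol and is varied as an assumption.

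**Formula** (one-sample normal approximation):

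Power = Φ{ [(p1 − p0)√n − 1.96 √(p0(1 − p0))] / √(p1(1 − p1)) }

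with √(0.03 × 0.97) = 0.1706 and √(0.054 × 0.946) = 0.2260.

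**Step 1: the protocol's own figure.** For n = 500: (0.024 × 22.361 − 1.96 × 0.1706) / 0.2260 = (0.5367 − 0.3343) / 0.2260 = 0.895, and Φ(0.895) = 81.5%. The stated >80% is reproduced. Two other methods agree at n = 500: a mid-p binomial test gives 81.2%, and a two-sample comparison with a comparator group 100 times larger gives 81.0%. A conventional exact binomial test (reject at 24 or more cases, upper-tail size 0.0179) gives 75.1%.

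**Step 2: smallest evaluable number for 80%.** n = [(1.96 × 0.1706 + 0.8416 × 0.2260) / 0.024]² = 477.7, so 478. That is 478/500 = 95.6% of the women. With 477 evaluable (23 of 500, or 4.6%, lost) power is just below 80%.

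**Step 3: 500 enrolled, assumed evaluable share.**

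| Share evaluable (assumed) | Evaluable n | Power |
|---|---|---|
| 100% | 500 | 81.5% |
| 90% | 450 | 78.0% |
| 85% | 425 | 76.1% |
| 80% | 400 | 74.0% |
| 70% | 350 | 69.4% |
| 60% | 300 | 64.1% |

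In reverse, 478 evaluable outcomes need 478/0.9 = 532 enrolled at 90%, 598 at 80% and 683 at 70%. All of these exceed the upper figure of 500.

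**Step 4: the accrual recorded in December 2019.** If all 260 were evaluable: (0.024 × 16.125 − 0.3343) / 0.2260 = 0.233, and Φ(0.233) = 59.2%. With 80% of 260 evaluable (208) power is 52.1%; with 70% (182) it is 48.1%.

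**Step 5: ratio detectable with 80% power, same formula and 3% background.** 1.78 at n = 500; 1.88 at 400; 2.03 at 300; 2.12 at 260; 2.29 at 200; 2.51 at 150.

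**The case against.** The strongest defence is that the sentence is conditional. It says what holds if 500 women are included, and on those inputs it is correct. A reader might infer that the power was miscalculated; Step 1 shows that it was not. It can also be said that the power sentence speaks of women included, and only the accrual sentence speaks of women enrolled. That is true, but the same section uses the same 500 for both and nothing defines the included women as evaluable ones. Figure 5-1 is not visible here. By its caption it plots power over several values of N, so lower power at lower N is partly disclosed, though still by women included.

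Three stronger readings are tempting and are not supported:

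- **That the registry cannot reach 500.** The 260 is a dated count in a registry not said to have closed. The 500 is an upper figure and four years is a minimum recruitment period. The count shows only that the condition was unmet in December 2019.
- **That power is really 75% even at 500.** This belongs to the conservative exact test. The protocol names no test, and the mid-p test gives 81.2%.
- **That the excess the protocol already reports is smaller than the one planned for.** Section 1 cites about 5% in post-marketing data. Against 3% the ratio is 1.67. Against the 2% to 4% background range in the same section it runs from 2.5 to 1.25, and against the EUROCAT 2.33% it is 2.14.

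Finally, the primary objective is descriptive, no decision rule depends on significance, and Section 1 already says that human data suggest an increased prevalence. This limits the risk of false reassurance. It does not remove the need for the one sample-size statement to refer to the set that is analysed.

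**Conclusion.** The point holds as a mismatch between the N of the power statement and the N of the primary analysis, together with an accrual sentence that is out of date. It is not an arithmetic error.

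The stated >80% applies only if at least 478 of 500 women are evaluable. Allowing for non-evaluable women costs a moderate amount by itself: power of 78% to 64% for an assumed share of 90% to 60%. The December 2019 count has the larger effect: at most 59% power, and a detectable ratio of about 2.1 instead of about 1.8, even with every woman evaluable.

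These sizes rest on a fixed 3% background, a two-sided 0.05 one-sample normal approximation, and evaluable shares that are assumed. The final evaluable number cannot be derived from the protocol.

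**What to change.** In Section 5.2 and Figure 5-1:

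1. Define N as evaluable prospective outcomes, meaning prospective cases with a known outcome that enter the risk denominator described at the end of Section 5.
2. State the test behind the power figure. No particular test is asked for.
3. Replace the sentence giving >80% at 500 women with power, detectable ratio and expected 95% confidence interval width over a plausible evaluable range, for example 150 to 500. Label the evaluable share as an assumption. As an illustration of interval width, 10 cases in 208 is 4.8%, with an exact 95% interval of 2.3% to 8.7%.
4. Update the accrual sentence with the 260 women recorded in Amendment 3.

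The cost is a few sentences and a redrawn figure. No extra enrolment is needed and the analysis does not change. The only disadvantage to the sponsor is a less favourable stated sensitivity.

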In animal models it was shown that fingolimod and its metabolites cross the placental barrier in pregnant rabbits (5.0 mg/kg orally) to a limited extent. The radioactivity concentrations in the fetuses were approximately 4-fold lower than in maternal blood. In rats, fingolimod increased post-implantation loss, and decreased the number of viable fetuses. In rabbits, fingolimod increased embryo-fetal mortality, decreased the number of viable fetuses and induced fetal growth retardation. The receptor affected by fingolimod (sphingosine 1-phosphate receptor) is known to be involved in vascular formation during embryogenesis. Fingolimod was teratogenic in rats, including persistent truncus arteriosus, ventricular septal defect [FTY720D-Summary of Safety Information]. The embryo-fetal effects in rats and rabbits occurred at maternal exposures similar to human therapeutic exposures. Available human data (post-marketing spontaneous reports and data from the Gilenya (fingolimod) pregnancy registry) suggest that use of fingolimod is associated with an increased prevalence of major congenital malformation in comparison to the general population.

The pregnancy status of females of reproductive potential should be verified prior to starting treatment with fingolimod.

As of 28-Feb-2019, in more than 600 prospective pregnancies with live births, still births or termination of pregnancy due to fetal anomaly with maternal exposure to fingolimod during pregnancy that were reported in post-marketing setting, the proportion of major congenital

malformations was approximately 5% (Investigator's Brochure, Edition 10, 2019). The prevalence of major congenital malformation in the general population is reported to be 2 to 3% in the European Union (EUROCAT) and 2 to 4% in the US (FDA Guidance for Industry, 2014).

The pattern of malformation reported for fingolimod is similar to that observed in the general population, wherein the common major malformations are:

- Congenital heart disease such as atrial and ventricular septal defects, tetralogy of Fallot
- Renal abnormalities
- Musculoskeletal abnormalities

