#### 3.4.7 Targeted follow-up

If one or more major or minor malformations are noted, it may be necessary to collect additional information. Signed release forms will be obtained by the enrolling HCP from the mother to acquire maternal and pediatric medical records and permission to contact the appropriate HCP, i.e., obstetrician/gynecologist, and/or pediatrician. Medical records will

allow for case verification. Each potential case will undergo clinical review to confirm status as a congenital anomaly case and to ensure the anomaly (or anomalies) are coded appropriately (i.e., accurately represent the defect or underlying diagnosis). Many terms are used clinically for the same structural or functional defect; therefore, the coding and grouping of anomalies is the key to a meaningful analysis of results. The clinical reviewer will determine what, if any, structural or functional abnormalities are present, if these are minor or major malformations and if there is additional information required to assess the case (e.g., pathology reports, medical records, assessment by neonatologist/pediatrician).

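### The malformation-risk formula divides anomalies by outcomes, so read literally an infant with several anomalies counts more than once above the line and once below it

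*Protocol*

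**What the plan says.** The formula stands near the end of the text that follows Section 5.2 of the protocol. The contents list calls this part Section 5.3, Classification of exposures and outcomes. Risk is obtained by "dividing the number of congenital anomalies associated with any pregnancy outcome by the sum of the number of live births without congenital anomalies" and affected outcomes; in full, the denominator is "the sum of the number of live births without congenital anomalies and any outcomes involving congenital anomalies".

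Other places bear on the unit of counting:

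- Section 5.1, on the planned estimate: "overall frequency (proportion, 95% confidence interval) of major malformations will be calculated". It is then compared with the frequency among infants in the external surveillance systems.
- Section 5.2, on the US reference: "3,030 infants with birth defects per 100,000 live births were reported by CDC (2010".
- Section 3.4.7, where each potential case is reviewed "to confirm status as a congenital anomaly case and to ensure the anomaly (or anomalies) are coded appropriately". One case may therefore carry more than one anomaly.
- Section 5.1, which has the only per-child grouping rule. It covers minor anomalies, reported as a single case "if three or more occur in the same child". Major malformations have no such rule.
- The paragraph before the formula: "details regarding coding and classification, and case definition, will be established in registry-specific clinical review procedures".

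**The concern.** A proportion needs each counted unit to be either affected or not, with the numerator contained in the denominator. The formula mixes units. An infant with a heart anomaly and a renal anomaly adds 2 to the numerator and 1 to the denominator.

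This is the only formula the protocol gives for its primary objective. The resulting rate is to be compared with external surveillance data and used to counsel patients. A numerator that can count one child repeatedly pushes the rate upward against an infant-level reference. A standard interval for a proportion would also be centred in the wrong place and would be too narrow.

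**Working it through.** **1. Units.** The numerator is a number of anomalies. The denominator is a number of outcomes. The planned estimate is a proportion, and the US comparator counts infants. The formula is the only one of these whose numerator is not a count of persons or outcomes. The ratio is not bounded by 1: two affected outcomes carrying three anomalies give 3/2 = 1.5.

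**2. The protocol's own figure.** Section 5.2 claims more than 80% power for 500 women, a 3% background, an 80% increase (0.03 × 1.8 = 0.054) and two-sided alpha 0.05. The one-sample normal approximation gives:

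- SE under the background rate: √(0.03 × 0.97 / 500) = 0.00763
- SE under the alternative: √(0.054 × 0.946 / 500) = 0.01011
- Power: Φ[(0.024 − 1.96 × 0.00763) / 0.01011] = Φ(0.895) = 81.5%

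The stated figure is reproduced. The calculation assumes one yes/no result per woman, which the formula's numerator is not.

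**3. Effect on the rate.** Let p be the true proportion affected and m the mean number of counted anomalies per affected infant. The formula then estimates m × p. The protocol does not give m, so 1.0 to 1.5 is an assumption. The multiplier does not depend on the number enrolled.

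**4. Effect on the interval.** The protocol names no interval method, so the exact (Clopper-Pearson) interval is assumed. The simulation used 400,000 runs, 500 outcomes and p = 3%, with anomalies per affected infant equal to 1 + Poisson(m − 1).

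| m (assumed) | Formula's expected value, 0.03 × m | Coverage of the true 3% | Coverage of the formula's own mean |
|---|---|---|---|
| 1.0 | 3.0% | 96.5% | 96.5% |
| 1.1 | 3.3% | 92.7% | 95.0% |
| 1.2 | 3.6% | 86.0% | 93.6% |
| 1.5 | 4.5% | 58.1% | 86.6% |

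The last column shows that the interval falls short even for the average number of anomalies per outcome. Take m = 1.5. The mean square number of anomalies per affected infant is 0.5 + 1.5² = 2.75. The variance of the count is 500 × (0.03 × 2.75 − 0.045²) = 40.2. A binomial count with the same mean has variance 500 × 0.045 × 0.955 = 21.5.

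**5. Illustration.** With 25 affected of 500, a per-infant count gives 5.0% (95% CI 3.3% to 7.3%). At m = 1.2 the formula gives 30/500 = 6.0% (4.1% to 8.5%). At m = 1.5 it gives 38/500 = 7.6% (5.4% to 10.3%), with 37.5 rounded to 38.

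**The case against.** The strongest reply is that this is loose wording. Section 5.1 calls the estimate a proportion, the denominator itself speaks of affected outcomes, Section 3.4.7 reviews cases, and the case definition is left to clinical review procedures. A case count was probably meant. Coding to the underlying diagnosis would also merge some related findings, and chromosomal and genetic disorders are handled apart. All of this stands, and it limits the likely size of the error. It does not change the arithmetic rule: no sentence restates the numerator as affected infants, and a deferred case definition does not say that each case counts once.

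Several stronger readings are tempting and are not supported:

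- **That the registry will raise a false signal.** If 24 or more of 500 were taken as the threshold, the chance of reaching it at a true 3% would go from 1.8% at m = 1.0 to 13.3% at 1.2 and 41.6% at 1.5. The protocol states no such decision rule; its objectives are descriptive. The 500 is an upper expectation of women, and 260 were enrolled at Amendment 3.
- **That the whole 80% target increase could be an artefact of counting.** This needs m = 1.8, which only restates the target ratio 5.4/3.0. It is not evidence about m.
- **That the formula is wrong because it is not limited to major malformations.** The primary objective covers major and minor malformations, so a generic formula is consistent with it.
- **That the denominator is wrong.** Section 1 reports its figure of about 5% "in more than 600 prospective pregnancies with live births, still births or termination of pregnancy due to fetal anomaly", whereas the formula leaves out unaffected stillbirths. The effect is small: adding an assumed 2 to 5 unaffected stillbirths to 25/500 gives 25/502 = 4.98% to 25/505 = 4.95%. Losses before 20 weeks enter only when anomalous, which could matter more, but the document offers no figure for them.

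The mismatch with the comparator is shown for the US reference only. The EUROCAT and worldwide figures in Section 5.2 do not say whether cases or anomalies are counted.

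**Conclusion.** The numerator's unit is wrong as written and should be fixed. Taken literally, the formula multiplies the true rate by the mean number of counted anomalies per affected infant. For a true 3% and an assumed mean of 1.0 to 1.5, it reads 3.0% to 4.5%, with no error at exactly one per infant. The coverage figures rest further on the exact interval, the assumed distribution of anomalies per infant and 500 outcomes.

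A reader might infer that children certainly will be counted repeatedly and that the registry's reported rate is therefore wrong. The document does not show that. It shows a rule that yields such a rate if applied as stated, alongside wording that points to a different intention. The established point is the numerator's unit alone, and its size cannot be determined from the protocol.

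**What to change.** Restate the numerator as the number of fetuses or infants (outcomes) with at least one confirmed congenital malformation, each counted once. Calculate it separately for major malformations, which is the rate to compare with MACDP and EUROCAT, and for minor ones under the grouping rule already in Section 5.1. Report the number of individual anomalies by type in a separate table.

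The main denominator can stay as it is. As a sensitivity line only, show the rate with all live births, all stillbirths and terminations for fetal anomaly as the denominator, listing anomalous losses before 20 weeks apart.

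The cost is one sentence in the protocol and matching table shells. No new data are needed. The reported rate may be slightly lower than under the literal formula.
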